#### **4. Subject Selection**

We will recruit and enroll dyads from MGH ICUs and stepdown floors. The majority of cardiac arrest (CA) survivors are initially cared for in the Heart Center Intensive Care Units and stepdown floors, while a minority are also cared for in the Neuro-ICU, Medical Intensive Care Unit, and Cardiac Surgical Intensive Care Unit, and corresponding stepdown floors.

During phase 1 of this study, the PI presented to staff from these ICUs and stepdown floors that care for CA survivors on the overall study aims, purpose, potential benefits to participants, and best ways to facilitate referrals.

Trained study staff will identify new CA survivors primarily through daily pre-screening of ICU and stepdown survivor rosters. We will also obtain referrals from the medical, nursing, or social work team members that are clinically caring for survivors and caregivers on service, whom the PI presented to during phase 1 of the overall study. A new CA survivor is defined as any survivor with a new diagnosis of "cardiac arrest" and documented loss of pulse in their medical record. Study staff will always confirm with a clinical team member about whether screened survivors might be appropriate study candidates before approaching to discuss our study.

Through pre-screening of ICU and stepdown floor patient rosters on Epic, our research assistant (RA) will identify CA survivors and add them to a "cardiac arrest admissions log" stored on REDCap of all CA survivors admitted to MGH during the study period. The cardiac arrest admissions log will serve to aid the RA in monitoring all currently admitted CA survivors' neurological exams to see if they will become eligible for the study. Specifically, the RA will conduct daily review of all currently admitted CA survivors' neurological exam daily as documented in the electronic medical record. The RA will specifically attend to the survivor's documented alertness, orientation, and speech output. The majority of cardiac arrest

admissions will not regain sufficient neurological function to participate in our open pilot, however, we will keep their basic clinical cardiac arrest characteristics in the admissions log for the duration of the study so that we can then compare our open pilot sample's characteristics to the characteristics of cardiac arrest admissions at MGH, and compare the cardiac arrest admissions at MGH to cardiac arrest patients in the United States. This information is routinely collected and reported in cardiac arrest research. We will need to be able to identify if our enrolled sample is representative of the greater population, and if not, we will need to report the disparities that exist in our enrolled sample.

Should the neurological exam demonstrate focal neurologic recovery (i.e., awake, alert and oriented), the RA will send a Voalte message to survivor's bedside nurse [or other clinician known to the survivor] to confirm recovery of focal neurological status and to ask the survivor for permission to be contacted by our team to explain the study (either in person or over phone if the survivor is discharged before we are able to approach).

Medical and/or social work partners caring for CA survivors that may benefit from our study have volunteered to provide basic information of our study (the same information listed on our study flyer, which they will give to such survivors) and ask the patients for their permission to refer them to us through the Voalte messaging system.

Once at the survivor's bedside the RA will explain the study and, if the survivor is interested in participating, will be asked to confirm that they have an informal caregiver (friend or family) that is primarily involved in their care and would be willing to participate. Once they confirm they have an informal caregiver, the RA will conduct emotional and cognitive screening with the survivor (Hospital Anxiety and Depression Scale for emotional distress and Short Form of Mini Mental State Exam for cognitive function). They will then ask permission to contact the survivor's informal caregiver and conduct the same emotional distress screening with the caregiver (either in person or over phone). Only one member of the survivor-caregiver dyad needs to screen in with emotional distress. If either dyad screens in with emotional distress, the RA will then proceed to obtain informed written consent either through paper form or via REDCap e-consent. Both participants that consent via REDCap will be emailed a copy of their signed consent form. The study team will keep track of all survivors and caregivers approached who refuse to participate and their reasons for refusal, as well as survivors that are not eligible to participate. We will also offer to provide survivors and/or caregivers that refuse to participate or screen out with a resource sheet for options to for emotional support should they feel they need it.

**Inclusion/Exclusion Criteria:** Out-of-hospital or in-hospital CA survivor (must have new diagnosis of "cardiac arrest" in electronic medical record from index hospitalization with documented loss of pulse) with an identified caregiver (identified by the survivor who is their primary source of emotional and functional support), 2) survivor must score  $\geq 4$  on Short Form of the Mini Mental State Exam for sufficient cognitive function for meaningful participation, 3) ability and willingness to participate in a hybrid in-person/live video or phone intervention, 4) English speaking adults (18 year or older), 5) at least one member of the dyad endorses clinically significant emotional distress during screening ( $>7$  on Hospital Anxiety and Depression Scale subscales). **Exclusion criterion:** 1) active psychosis, mania, substance dependence, or suicidal intent or plan.

We are excluding non-English speakers from our open pilot as our intervention development studies and the original Recovering Together intervention were conducted with fluent English speakers only. Delivering this intervention in a different language, using a translator, would be inappropriate as content may not be sensitive or relevant for non-English speakers. We do plan to conduct future cultural adaptation studies of our intervention, including conducting qualitative studies with end-users that are non-English speakers. Unfortunately, we have insufficient funds from the current grant to conduct such studies.

**The following strategies will be used to recruit and retain ethnic/racial minorities:**

**As part of the recruitment protocol:**

- We will prioritize recruiting racial and ethnic minorities with the goal of increasing inclusion of minorities. Our goal is to follow the race and ethnicity distribution of the USA and recruit at least 38% racial and ethnic minorities.
- Through our presentations to ICU and stepdown physicians, nurses and study staff, we will encourage engaging in trainings around cultural competence and internalized racism to ensure interactions with survivors are able to be rooted in trust and respect.
- We will be flexible in scheduling to address logistical barriers to participation.
- We will consult the “Community Access, Recruitment, & Engagement” Research MGH group to promote recruitment and retention of diverse families.

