## 2. Specific Aims and Objectives

**Aim 1: Refine RT-CA.** We will conduct a single-arm open pilot of RT-CA (N=5 dyads) to evaluate initial feasibility and acceptability using exit interviews and pre-post assessments.

Findings from Aim 1 will then inform the next iteration of the RT-CA manual and feasibility trial.

**Aim 2: Conduct medical record review** of all admitted cardiac arrest patients at MGH during the study period (N = 200-400). We will collect basic cardiac arrest clinical data on these patients to determine the representativeness of our sample in Aim 1 to all cardiac arrest admissions at MGH and the United States.

Findings from Aim will inform recruitment gaps, if any, and contextualize the recruitment pool at MGH relative to the United States.

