## 3. General Description of Study Design

We are proposing an open pilot trial of RT-CA with 5 CA survivor-caregiver dyads. All dyads will undergo the 6-session intervention. The first session will be at the bedside (unless the survivor is discharged before session 1 takes place, at which point we will meet over Zoom or telephone (Doximity)). The remaining sessions will be conducted over Zoom or telephone (Doximity) depending on participant preference.

Parallel to our open pilot, we propose to conduct medical record of all admitted cardiac arrest patients at MGH during the study period and maintain them in a study log (N = 100-300). As part of our recruitment efforts (see sections 4 and 5), we will pre-screen Epic ICU and stepdown floor rosters in order to identify all cardiac arrest patient admissions, who could be eligible for our open pilot. By including all admissions into a study log we will be able to 1) monitor cardiac arrest patients' mental status during their hospital stay to see if they will become eligible for our open pilot and 2) determine the representativeness of the open pilot sample's cardiac arrest clinical characteristics.

We will need to access the medical records of all cardiac arrest admissions to monitor them throughout their stay in the hospital. If the patient recovers good neurological status, they may be eligible for our study, at which point we will follow our recruitment and enrollment procedures as detailed below. There is no guarantee that a patient with cardiac arrest recovers neurological status, so we will need to conduct daily pre-screening of their neurological exam until they become potentially eligible or are discharged.

Additionally, we will need to collect basic cardiac arrest clinical data of all cardiac arrest admissions in order to contextualize our study sample in the context of cardiac arrest admissions at MGH and the US overall. This information is routinely collected and reported in cardiac arrest research. We will need to be able to identify if our enrolled sample is representative of the greater population, and if not, we will need to report the disparities that exist in our enrolled sample.

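### Aim 2 is to judge representativeness and the plan sets a 38% minority goal, but race and ethnicity are not among the variables logged for all admissions

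*Combined protocol and SAP*

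**What the plan says.** Section 4, in the list of recruitment strategies, says "We will prioritize recruiting racial and ethnic minorities with the goal of increasing inclusion of minorities" and gives the goal as to "follow the race and ethnicity distribution of the USA and recruit at least 38% racial and ethnic minorities". It does not say whether the 38% applies to survivors, dyads or individuals.

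Section 2 gives the purpose of the record review: "to determine the representativeness of our sample in Aim 1 to all cardiac arrest admissions at MGH and the United States". It adds that the findings "will inform recruitment gaps, if any, and contextualize the recruitment pool at MGH relative to the United States". Section 3 (repeated in Section 4) says that the team must find out whether the enrolled sample is representative, and "if not, we will need to report the disparities that exist in our enrolled sample".

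Section 6 lists what is taken from the record of every logged patient under the requested waiver of consent: arrest location, time to ROSC, initial rhythm, age and sex. The same items are logged for pilot patients. Enrolled participants also complete a Demographics form at baseline, whose content is not itemised. Section 4 says that refusals, reasons for refusal and ineligible survivors are tracked, without saying what is recorded about them.

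Section 9 plans chi-square and Wilcoxon rank sum tests of clinical arrest characteristics, comparing the pilot with MGH admissions and with published US figures. It describes no analysis of race or ethnicity and no check of the 38% goal.

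**The concern.** The admissions log is the plan's only instrument for judging who the pilot represents. It omits a characteristic on which the plan sets a numerical representation goal and which Section 4 treats as a known recruitment problem.

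If few minority dyads enrol, the team will want to know why. Few minority patients may have been admitted. Few may have recovered enough, or met the language, caregiver and distress criteria. They may not have been approached, or they may have declined. These explanations call for different responses in the next trial, and a log without race and ethnicity cannot tell them apart. The comparison of the MGH pool with the US, which does not depend on the five dyads at all, is lost on the same characteristic.

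**Working it through.** The plan gives no sample size, power or alpha for this point, and the 38% has no derivation, so there is no figure of the plan's own to reproduce. The check sets the purpose of Aim 2 against the variable list, then asks what the enrolled count and the log could each contribute.

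**1. Purpose against variables**

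| Characteristic | Logged for all admissions (Section 6) | Pilot can be compared with MGH admissions |
|---|---|---|
| Arrest location, time to ROSC, initial rhythm | yes | yes |
| Age, sex | yes | yes |
| Race, ethnicity | no | no |

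**2. What the enrolled count says alone.** Inputs: 5 dyads (Section 2) and the 38% goal (Section 4).

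- Counting survivors: 0.38 × 5 = 1.9, so the goal needs 2 of 5. Counting individuals: 0.38 × 10 = 3.8, so it needs 4 of 10.
- Goal missed although the true share is 38%, n = 5: 0.62^5 + 5 × 0.38 × 0.62^4 = 0.092 + 0.281 = 0.372. For n = 10, the binomial probability of 3 or fewer is 0.434.
- Goal met although the true share is only 20% (assumed), n = 5: 1 − 0.8^5 − 5 × 0.2 × 0.8^4 = 1 − 0.328 − 0.410 = 0.263. For n = 10 it is 0.121.
- Exact (Clopper-Pearson) 95% intervals: 0 of 5 gives 0 to 52%, and 2 of 5 gives 5 to 85%. Both contain 38%.

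**3. What the log could add.** The log size is 200-400 in Section 2 and 100-300 in Section 3, so the range 100 to 400 is used. The minority share among admissions is not given; 15% to 50% is assumed. If the log is treated as a sample of the MGH pool, the 95% half-width is 1.96 × √(p(1 − p)/n), in percentage points:

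| Assumed share | n = 100 | n = 200 | n = 400 |
|---|---|---|---|
| 15% | 7.0 | 4.9 | 3.5 |
| 25% | 8.5 | 6.0 | 4.2 |
| 50% | 9.8 | 6.9 | 4.9 |

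If the log captures every admission, as intended, it is a count for the study period and sampling error matters less still.

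**4. What the log could not add.** Adding the fields would not make a test of the pilot against admissions useful. This uses Fisher's exact test, two-sided at an assumed 0.05, of 5 enrolled survivors against the rest of a log of 100 to 400.

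- With 0 of 5 minority survivors and a log share of 38%, p is about 0.16. It falls below 0.05 only when the log share exceeds about 51-54%.
- If the true enrolled share is 38% and the log share is 15%, rejection needs 3 or more of 5, so power is 1 − 0.7165 = 0.28. For log shares of 20%, 25% or 30% it needs 4 or more, so power is 1 − 0.9274 = 0.07.

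Five survivors limit that comparison, whatever the log size.

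**The case against.** The strongest defence is scope. Wherever the documents describe the data for Aim 2, they speak of clinical arrest characteristics, and racial representativeness is never named as an output. This stands to the extent that the plan breaks no explicit promise. But age and sex are already in the log, so demographics are not out of scope, and recruitment gaps and disparities are stated purposes broader than arrest physiology.

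A second defence is data minimisation. Section 5 justifies the waiver by the small amount and non-sensitive nature of the information, and Section 12 limits collection to what is necessary. This is a cost that the amendment must meet, not a bar.

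A third is that five survivors cannot support a comparison. That is right for a test and is why the fix is a table. It does not touch the description of the admitted pool or the comparison of MGH with the US.

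Three stronger readings are tempting and are not supported:

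- A reader might infer that a shortfall against 38% would go unseen. The goal is set against the US distribution, so a crude shortfall could be read from enrolled dyads if the Demographics form records race and ethnicity. Nor is 38% the only number attached to recruitment: the benchmark table in Section 9 asks for more than 70% of eligible dyads to participate.
- A reader might infer that prioritisation makes the pilot differ from admissions by design. Section 4 describes training, flexible scheduling, consultation and trust-building, with no quota or selection rule. Such outreach might equally bring the pilot closer to the pool.
- A reader might infer that differences in age or rhythm would be confounded with prioritisation. Nothing in the documents shows this, and five survivors could not settle it even with race logged.

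**Conclusion.** The point holds for Aim 2. Followed exactly, the plan yields no comparison of the pilot with MGH admissions, or of the MGH pool with the US, on race and ethnicity. It also cannot locate the source of a shortfall against 38%. The enrolled count does not fill the gap: judged on five survivors, the goal is missed 37% of the time at a true 38% and met 26% of the time at a true 20%.

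The consequence is limited. The feasibility and acceptability outcomes of the pilot are unaffected, and the missing information matters mainly for planning recruitment to the next trial. The change is worth making because it is cheap and serves a stated aim.

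The verdict rests on the Section 6 list being complete. The remedy further assumes that the Demographics form records race and ethnicity, that the chart holds them for most admissions, and that the published US source reports them. The documents state none of these. If the tracking of refusals and ineligible survivors does record race, part of the pathway could be reconstructed, but the admitted denominator would still be missing.

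**What to change.** - **Section 6:** add race and ethnicity, where recorded in the chart, to the variables logged for all admissions.
- **Section 5:** extend the waiver request to these two fields, and justify them by the representativeness purpose of Aim 2 against the section's present argument that little and non-sensitive information is taken.
- **Section 9:** tabulate survivors admitted, eligible, approached and enrolled by race and ethnicity, with missing entries as their own category. Give exact intervals and no significance test, because only five survivors are enrolled. Note beside the table that enrolment was subject to planned minority outreach.
- **Section 4:** state whether the 38% goal counts survivors, dyads or individuals. Keep the goal and the outreach as they are.

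The cost is two more chart fields per logged patient and a waiver amendment. Chart entries for race and ethnicity may be missing or misclassified, so the table should be read with that in mind.

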**In collaborations with providers and staff:**

- We will explain underrepresentation of minority participants in research and collaborate on how to address this issue.
- Research indicates that participants are more likely to enroll if the study is presented to them by a previously trusted individual such as their care providers. We will encourage attending physicians, bedside nurses, and social workers to recommend our study when they are treating emotionally distressed survivors and/or their informal caregivers.

**In interactions with participants:**

- We focus on trust-building with potential participants during recruitment because mistrust of research/health care establishments can be a barrier to minority participation. We will clearly explain the research study and ensure that families have all information they need to decide whether to participate in the study.
- We will prioritize the safety and personal health of dyads, clearly explaining the measures taken in study protocol to protect them and explaining the supports available to them during study participation.
- We will ask about participant concerns and answer any questions that may have.
- We will emphasize how research participation benefits the broader good, including their own communities.

## 5. Subject Enrollment

We are requesting a waiver of consent for logging the clinical cardiac arrest variables for all cardiac arrest admissions. These variables are already listed in their electronic medical record, and the review of such records is for very limited information. Further, the variables are not sensitive in nature. We will collect such variables and log them on a hospital-based, secured data capture software (REDCap).

For survivors that meet criteria for our open pilot as discussed in section 4, once a potential survivor has been identified and approved by the clinical team, and has granted permission for us to contact them, a member of the study team will approach the survivor as soon as possible.

Survivors and caregivers that wish to participate will complete written informed consent. All potential participants will be given a paper informed consent form, a tablet to complete e-consent through REDCap, or will be emailed the consent form via REDCap depending on their preference. All participants will be given the opportunity to ask any questions. These discussions will cover the potential risks and benefits of participation, as well as information regarding who participants can contact for further questions. Potential participants will also be informed that participation is voluntary, that they can refuse to answer any

questions, and they can withdraw from the study at any time. They will be informed that refusal to participate in the study will in no way impact their own or their loved one's medical care.

Participants will be given the option to receive text messages with reminders to practice skills (active intervention only) as well as survey invitations, and study contact information (including that of the IRB) in case questions arise at a later time. The text messages will be sent via Twilio, a third party, Partners-approved, web service that integrates with REDCap to send survey invitations over SMS text messaging.

Once all questions have been answered, participants interested in participating will return a physical signed consent form or will sign virtually via e-consent. Study staff will keep all informed physical consent forms in a cabinet under lock and key.

If the caregiver subject is unable to be at the bedside in person for consent for their own participation, then a study staff member will telephone call the caregiver and explain consent procedures over the phone. In this case, we will email the consent form to the caregiver subject through REDCap secure data collection system while on the telephone with them, and if they agree to participate, the caregiver subject will e-sign consent for their own participation.

All subjects will be given baseline psychological and behavioral assessments that will assess depression, anxiety, PTSD symptoms, and other psychological constructs. All assessments will be administered using the REDCap secure data collection system or via paper and pencil to be entered into REDCap later by study staff.

## 6. STUDY PROCEDURES

**See below for the complete open pilot schedule.**

**Study Intake (1/2 hour)**

After completing informed consent, participants will fill out several questionnaires online or in person, through REDCap.

**Weekly Sessions 1-6**

The intervention will have 6 sessions, delivered either at bedside or over Zoom/telephone, depending on participant preference. Zoom is a free and secure online videoconferencing software program that is currently used to provide care for patients at MGH.

All sessions will be audio-recorded to use in clinical supervision (e.g., problem-solving challenging cases) and to check study therapist competency and fidelity. Dyads will receive a Home Practice reminder text 24 hours after their previous session each day until their next session.

Sessions focus on developing skills to cope with and manage CA-related stressors. The sessions were adapted from an existing MGH trial (Recovering Together) and from MGH CA survivor-caregiver feedback. Specifically, we conducted qualitative interviews with survivor-caregiver dyads based on their needs for emotional support. We further queried them on feedback of proposed intervention content.

The 6 sessions are listed below. We will make adjustments to the program and sessions as needed based on dyads' post-program feedback:

